9.3 Interim analyses and Stopping Rules

There are no plans to conduct an interim analysis. The study team will collaborate with the DSMB to define thresholds at which differential rates of safety events by treatment group warrant consideration of suspending patient accrual or modifying intervention delivery.

9.4 Outcomes

9.4.1 Primary outcome

The primary outcome will be CI detection (H1). CI detection will be a binary outcome calculated from EHR data and defined as occurring when an ICD-10 diagnostic code for CI is documented at outpatient or inpatient encounters, or added to the problem list, between the index visit date and the end of the observation period, inclusive.

9.4.2 Secondary outcomes

A secondary outcome will be clinician-reported confidence in management of CI care (H2). The pre-and post-implementation clinician surveys in both study arms will include a series of Likert-scale survey items based on previous literature to assess confidence to correctly assess and diagnose CI.[14, 27] Items will ask about confidence in diagnosis and management of CI care generally and will include items about specific elements such as conducting appropriate testing and patient and care partner education. Items will be analyzed individually, and composite measures of confidence will be considered.

Another secondary outcome will be health care utilization among accrued patients with HealthPartners insurance (H3). Indicators of any use of emergency room (ER), inpatient or both facility types between the index visit and of the observation period, inclusive, will be calculated from data extracted from insurance claims databases. Additionally, the combined costs of ER and inpatient care delivered will be extracted as paid amounts for facility and professional services on ER and inpatient days.

Patient and clinician characteristics that could moderate the effectiveness of the CI-CDS system on these primary and secondary outcomes will also be extracted from the EHR and clinician surveys. EHR-based data include patient encounters (number and type), demographics (e.g., age, gender, race, ethnicity), social determinants of health (e.g., insurer, area deprivation index score for home address, median education for Census tract of home address, country of origin, need for interpreter) and comorbidities present at index (e.g., diabetes, cardiovascular disease, mental illnesses, substance use). Potential clinician moderators include clinician self-reported years in practice, sex, provider type and specialty.

The effectiveness of the CI-CDS system on several exploratory outcomes will also be assessed. These exploratory outcomes include clinical actions documented in patient charts or the EHR (e.g., referrals to community resources; documentation of care plans, release of information, caregiver identification or recommendations for managing stressful symptoms or safety); clinician attitudes (e.g., perceived control, attitudes about CI, perceived norms) or perceptions of CI-CDS (e.g., usefulness, intentions to treat patients with CI) reported in the post-implementation clinician survey; and patient or caregiver experiences discussed in the patient/caregiver dyad interviews about assessment for CI (e.g., addressed or unaddressed concerns about memory; benefit or harm of screening; feelings of preparedness, support, distress among newly diagnosed patients).

We will use the CI-CDS metadata (e.g., display, print, click rates for CI-CDS features or patient educational or resource materials) and the EHR (e.g., Quick Orders for cognitive assessment, labs, brain imaging, referrals, medications for cognition benefits or symptom management) to track clinician use of the CI-CDS system and compliance with suggested actions.

9.5 Data Analyses

9.5.1 Primary analysis

The H1 sample will consist of primary effectiveness site patients accrued from the CI-CDS and UC clinics who are at elevated risk for CI but without a CI diagnosis at index. The primary outcome is defined as at least one CI diagnostic code or CI diagnosis entry on the problem list at any time between the index visit and the end of the observation period (at least 12 and up to 24 months post-index), inclusive. H1 will be tested using a generalized linear mixed model (LMM) to account for clustering within randomized clinics and normalize the binary outcome via a distribution-appropriate link function (e.g., logit, log). Clinic-randomized treatment group and any patient covariates (e.g., age at index visit, sex, MC-PLUS risk score at index visit) will be treated as fixed effects.

Descriptive statistics will be calculated on all pre-intervention patient variables across all accrued patients, by treatment group and by clinic to ensure that key patient characteristics related to the risk of CI or its diagnosis (i.e., age, sex, comorbidities) are balanced across treatment arms. Imbalanced patient characteristics will be considered for inclusion as covariates in the primary analyses.

For H1, we will fit a generalized LMM in which the binary post-index CI diagnosis outcome will be predicted via a link function from fixed effects for the clinic-randomized predictor, γ_{10} , and patient covariates, γ_{0*} , and a random clinic intercept, v_j , such as:

$$\text{logit}(\text{diagnosis}_{ji}) = \gamma_{00} + \gamma_{10}\text{CI-CDS}_j + \gamma_{0*}(\text{pt covars})_{ji} + [v_j].$$

Parameter γ_{10} is expected to be positive and statistically significant, indicating that accrued patients in clinics randomly assigned to CI-CDS are more likely to receive a CI diagnosis in the observation period than patients in UC clinics, accounting for fixed effects and random clinic variation.

In a second model, we will add a fixed coefficient that represents time elapsed between the index visit and the first EHR-documented CI diagnosis, or zero for those lacking a CI diagnosis, and the interaction between treatment group and time. The time covariate will be coded as (days since index)/365 so that it quantifies the predicted annual change in CI diagnosis rates. The time parameter is expected to be near zero and not statistically significant. Should the time elapsed between index and CI diagnosis differ by treatment group, log (observation time) may be included as an offset in the primary analysis.

This same analytic approach will be used to estimate the CI-CDS system treatment effect at the replication site. There are no plans for a pooled analysis across the primary effectiveness and replication sites, nor to implement alpha-sparring techniques. The determination of CI-CDS effectiveness will rest on the results of the primary analysis at the effectiveness site.

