4. SELECTION AND ENROLLMENT OF PARTICIPANTS

Primary care clinics

The OCHIN Lead Co-Investigator will collaborate with the HealthPartners Co-PIs to identify eligible service areas (groups of related clinics) that will be randomized 1:1 to the CI-CDS or UC treatment group. OCHIN will enroll at least three service areas with at least 10 total constituent primary care clinics as CI-CDS replication sites; a similar number of service areas and primary care clinics will serve as usual care (UC) replication sites. Stratified randomization by SA size may be used to balance the number of constituent clinics in each treatment group. Replication site clinics must currently have access to cardiovascular (CV) Wizard to be eligible for randomization. Service areas were chosen as a unit of randomization to avoid intervention contamination within groups of these highly related clinics.

CI-CDS and UC service areas will be approached for participation in the study. Service areas, and their constituent clinics, that agree to participate by allowing full or silent implementation of the CI-CDS system will be considered enrolled.

Recruitment will be conducted by the OCHIN study team, with support as needed from the HealthPartners staff. Eligible service areas and their clinics will be sent an introductory recruitment email with relevant study-related information, such as outlining the goals of the study, the CI Wizard tool, and an invitation to participate. Study team staff will follow-up via email, telephone, or video conference platform to answer any questions, provide demos of CI Wizard CDS, and/or share additional information regarding participation with service areas that are interested, as appropriate.

Once a service area agrees to participate, OCHIN will follow up with a Memorandum of Understanding (MOU) that outlines participation expectations, a timeline for study activities, and details regarding compensation. These MOUs will be signed by OCHIN and leadership at the participating service areas prior to starting study activities. Service areas will receive an impact payment of up to \$3000 as compensation for the time spent engaging in study activities. This impact payment will be distributed by OCHIN and is provided to the service area and not to any individual within the service area or clinic.

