9. STATISTICAL CONSIDERATIONS

9.2 Sample Size and Randomization

Operational considerations at the replication site make clinic-randomization impractical. To accommodate these considerations, randomization will be conducted by service area rather than clinic. Service areas eligible for randomization are those that currently have access to CV Wizard.

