10. DATA COLLECTION AND QUALITY ASSURANCE

The sole data source for the replication site is OCHIN EHR data. No claims-based data are available, nor will survey data be collected, at the replication site. The following EHR data will be collected from the CI-CDS tool and will be saved in an operational repository at HealthPartners. Individual and clinic identifying information, including patient name, date of birth, clinician name/ID, clinic name/ID, and department ID will then be removed from the data set and replaced by a random identifier prior to saving it into the research data repository.

Clinic-level data	Clinic name and/or ID, department ID, clinician name and/or ID
Patient-level data	Patient name (purged nightly), date of birth (purged nightly), age, gender, race, diagnosis (with dates), lab values (with dates), vitals (with dates), allergies (with dates), Rx (with dates), assessment results (with dates)
CI Wizard use data	Wizard print rates and click rates

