Each patient will accrue into the study at their index visit. The index visit is the first visit during the accrual period at a randomized clinic at which a patient meets all intervention eligibility criteria. The index visit date will mark the beginning of each accrued patient's observation period. Patients will have up to 24 months of observation period, and those with an index visit near the end of the accrual period will have an approximate 12-month observation period.

Following intent-to-treat (ITT) principles, all accrued patients will be attributed to the clinic at which their index visit took place, and to the treatment group to which their clinic is randomly assigned. Patients who have an index visit, and thus have accrued into the study, may have additional visits at randomized clinics prior to the end of the intervention period. The CI-CDS system is programmed to assess intervention eligibility at all visits at all randomized clinics in both treatment groups for the duration of the intervention period, and to display tailored CI-CDS for eligible post-index visits in CI-CDS clinics only.

[figure not shown]
In addition to the primary effectiveness trial, the CI-CDS system will be implemented and evaluated in a separate, independent health care system. The replication site study design will be similar in that up to 30 primary care clinics will be randomized to a CI-CDS or UC treatment group. The CI-CDS system will be fully implemented in CI-CDS clinics and partially implemented in UC clinics (i.e., working in the background to collect data but not visible to clinicians). Patients will accrue into the study at index visits over a 6-month accrual period, with an approximate 6-month observation period for the last accrued patient, resulting in a ~12-month intervention period.

Structural differences between the effectiveness and replication sites require that processes such as randomization, outcome measurement, and analysis be implemented differently at the replication relative to the effectiveness site. Information about these processes at the replication site will be provided in a site-specific supplemental analysis plan.

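### Protocol 9.5.1 gives the replication site a model with only a clinic intercept, although OCHIN randomises service areas, and SAP 2.1 defers the analysis to a supplement without naming a model

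*Protocol*

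**What the plan says.** **Model.** Protocol 9.5.1 states: "H1 will be tested using a generalized linear mixed model (LMM) to account for clustering within randomized clinics". The displayed equation has fixed effects for arm and patient covariates and one random term, the clinic intercept. The section then says of OCHIN: "This same analytic approach will be used to estimate the CI-CDS system treatment effect at the replication site".

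**Randomised unit at OCHIN.** Section 9.2 of the replication appendix (Protocol 15.5) says "randomization will be conducted by service area rather than clinic". Protocol section 2 agrees. Section 4 of the appendix gives the reason: "Service areas were chosen as a unit of randomization to avoid intervention contamination within groups of these highly related clinics". It also gives the size: "OCHIN will enroll at least three service areas with at least 10 total constituent primary care clinics as CI-CDS replication sites", and "a similar number of service areas and primary care clinics will serve as usual care (UC) replication sites". Stratification by service-area size is optional. The appendix amends parts of sections 9.2 and 9.4 but has no entry for 9.5.

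**SAP.** SAP 2.1 says that structural differences make a different randomisation and analysis necessary at the replication site, and continues: "Information about these processes at the replication site will be provided in a site-specific supplemental analysis plan". The same section still describes up to 30 clinics being randomised there. The supplement is not among the documents.

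**Data fields.** Section 10 of the appendix lists the clinic-level items as "Clinic name and/or ID, department ID, clinician name and/or ID", with identifiers replaced by random ones in the research data. No service-area field is listed.

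**Role.** Protocol 9.5.1 plans no pooling across sites and bases the judgement on effectiveness on the main site alone.

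**The concern.** In a cluster-randomised trial the arm effect has to be judged against variation between the units that were randomised. At the main site that unit is the clinic and the model fits. At OCHIN the clinics of one service area all receive the same arm together, and the protocol itself treats them as closely linked. If areas differ in their diagnosis rates for reasons unrelated to the intervention, a model with only a clinic intercept counts each clinic as independent evidence. The standard error is then too small, and the reference distribution has too many degrees of freedom.

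At stake is what the replication can show. With few service areas per arm, a chance difference between areas could be reported as a repeated effect.

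**Working it through.** **Inputs from the documents.** Minimum of 3 areas and 10 clinics in the CI-CDS arm, similar in UC (appendix section 4). Table 2 of Protocol 9.2.2 uses 22, 26 or 30 clinics, 60 patients per clinic, clinic ICC 0.03 to 0.05, UC rate 4% to 12%, two-sided 0.05 and power 0.80.

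**Assumption.** The share of the between-clinic variance that lies between service areas is not in the documents. It is varied below.

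**Step 1: the plan's own figure.** For the median cell of Table 2 (26 clinics, ICC 0.04, UC 8%):
- N = 26 × 60 = 1,560
- design effect = 1 + 59 × 0.04 = 3.36
- effective N = 1,560 / 3.36 = 464.3, about 232 per arm
- 8% versus 16.5% needs 233 per arm for 80% power

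The stated 16.5% is reproduced. This calculation counts clinics and has no service-area term.

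**Step 2: degrees of freedom at the minimum size.** By clinic: 20 − 2 = 18, critical t 2.10. By service area: 6 − 2 = 4, critical t 2.78. The documents name no degrees-of-freedom method, so these describe the two levels and not a stated choice.

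**Step 3: variance ratio.** Split the ICC into an area part rs and a clinic part rc, with rs + rc = 0.04 and residual 0.96. With 3 areas, 10 clinics and 60 patients per clinic in each arm:
- true variance ∝ rs/3 + rc/10 + 0.96/600
- variance if clinics are taken as independent ∝ 0.04/10 + 0.96/600 = 0.0056

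The approximate error is 2 × [1 − Φ(1.96/√ratio)]:
- rs = 0.005: 0.00677 / 0.0056 = 1.21, error 7.5%
- rs = 0.01: 0.00793 / 0.0056 = 1.42, error 10.0%
- rs = 0.02: 0.01027 / 0.0056 = 1.83, error 14.8%

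**Step 4: simulated null.** UC rate 8%, 60 patients per clinic, total ICC 0.04, 20,000 trials per cell, two-sample t test on clinic proportions with clinics minus 2 degrees of freedom:

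| Per arm | area share 0 | 10% | 25% | 50% | 100% |
|---|---|---|---|---|---|
| 3 areas, 10 clinics | 4.3% | 6.5% | 9.7% | 15.2% | 28.8% |
| 3 areas, 13 clinics | 4.7% | 7.3% | 11.8% | 19.3% | 35.6% |
| 6 areas, 13 clinics | 4.8% | 5.8% | 7.3% | 10.1% | 16.7% |
| 8 areas, 13 clinics | 4.7% | 5.0% | 6.2% | 8.0% | 12.2% |

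A t test on service-area means (4 degrees of freedom with three areas per arm) gave 4.1% to 5.0%.

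**Step 5: the planned type of model.** A maximum-likelihood logistic model with a random clinic intercept and a t reference (3 areas, 13 clinics per arm, 500 trials per cell, Monte Carlo error about 1 to 2 points) gave 7.2%, 7.8%, 12.0% and 24.4% at shares of 0, 10%, 25% and 50%. It already exceeds 5% with no area variance, so its 7.8% at a 10% share cannot be put down to the missing area term. The rise at 25% and 50% can.

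**The case against.** The strongest reply is that the sponsor has already changed course. SAP v1.0 (7/25/2025) postdates Protocol version 5 (May 08, 2025) and says the replication analysis will be done differently. In addition, 9.5.1 refers to an approach and offers its equation as an example, so a random effect for whichever unit was randomised is a possible reading. A reader might infer from 9.5.1 that the final test will treat clinics of one area as independent. The documents do not establish that, and this part of the reply stands. It does not settle the matter: the SAP names no model, still calls clinics the randomised unit, and leaves the protocol sentence in force.

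A reader might also take an error near 20% as the expected result. That needs the minimum of three areas per arm, 13 clinics per arm and half of the ICC between areas. Three is a floor, and no document gives the area share. With six or eight areas per arm the inflation is modest.

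The absent service-area field is weak evidence. The list covers what the CI-CDS tool collects, and does not show the treatment arm either. Clinic identifiers are collected, and each clinic's area is known from randomisation. The link may well be available, so it needs confirming and should not be called missing. Stratification is optional, so the lack of a stratum term is not in itself an error.

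Finally, effectiveness is judged at the main site, where clinics are both randomised and modelled. That is correct and limits the consequence to the replication.

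**Conclusion.** The point holds as a conflict between documents and an unspecified replication analysis. The only replication model stated has no term for the randomised unit, and the later SAP promises something different without saying what.

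For a clinic-level t test at a total ICC of 0.04, with 10% to 50% of it between areas, the type I error is about 6.5% to 19% with 3 areas per arm (10 to 13 clinics) and about 6% to 10% with 6 areas per arm (13 clinics). It is about 4% to 5% if areas do not differ, and higher if areas carry most of the variance. These figures rest on the assumed area share and the assumed number of areas. The main-site test of H1 is not affected.

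**What to change.** Replace the replication sentence in Protocol 9.5.1, and put the same specification in the supplemental plan:
- Account for service area as the randomised unit, by a random service-area effect with clinic nested within it or by a service-area-level analysis.
- Include the size stratum if stratification is used.
- Test the arm effect on service-area degrees of freedom: areas minus 2, less any stratum terms.
- Use a permutation test only as a check, and only where it can reach 0.05. With 3 versus 3 areas there are C(6,3) = 20 allocations, so the smallest two-sided p is 2/20 = 0.10. Stratification reduces the allocations further.
- Correct the description of the randomised unit in SAP 2.1, and confirm that a coded service-area identifier is kept in the research data set.

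The work is wording and one confirmed field. The real cost is a wider interval and lower power. For 8% versus 16.5% with 26 clinics and ICC 0.04, a service-area-level t test has simulated power of about 47%, 42%, 34% and 28% at area shares of 0, 10%, 25% and 50% with three areas per arm, and about 60% down to 49% with six. The clinic-level t test reaches only about 67% in the same simulation, so part of the gap from 80% comes from the simulation model and the t reference. Replication power should be restated with the service area as the cluster.

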9.5.2 Secondary analyses

Treatment effectiveness may vary as a function of contextual factors or patient characteristics.

Secondary H1 analyses will add fixed parameters to the H1 model that assess contextual factors (e.g., area deprivation index score for home address, median education for Census tract of home address) or patient characteristics (e.g., socioeconomic status, gender, pre-intervention CI risk) as main effects and in interaction with the CI-CDS indicator to assess whether the CI-CDS intervention is differentially effective (i.e., treatment heterogeneity) across patient subgroups, or relatedly, whether the CI-CDS intervention can reduce pre-intervention disparities in CI care.

9.5.3. Secondary outcomes

H2 predicts that clinicians practicing in CI-CDS relative to UC clinics will report more post-implementation confidence in diagnosing and managing CI. We will also use a LMM approach for the H2 analyses. The distributional properties of the confidence and management composites calculated from post-implementation clinician survey data will inform how to specify the distribution and link functions for these variables (e.g., normal-identity, Poisson-log, binomial-logit, binomial-log, multinomial-cumulative logit). The fixed CI-CDS parameter and random clinic intercept from the H1 model will be retained, and a fixed parameter for the outcome value reported in the pre-implementation clinician survey will be added. Exploratory analyses will assess whether the relationship between CI-CDS and either of these outcomes is more pronounced among clinician subgroups (e.g., clinician type).

H3 predicts that patients accrued from CI-CDS clinics will have lower post-index health care utilization. Anticipating a zero-mass of patients with no emergency department or inpatient costs, we will employ a 2-part model to test H3.[86] In the first part, the probability that patients will experience one or more emergency department visits or inpatient stays will be assessed using logistic regression in the same form as was used for H1. The second part will employ a generalized linear model (GLM)[87, 88] allowing clustering by clinic and controlling for demographics and baseline risk. Such analyses often specify a gamma distribution for health care expenditures with a log link function of the explanatory variables. We will choose the distribution family based upon the data using a modified Park test and choose the link function using a Box-Cox test.[89] If we observe a statistically significant reduction in emergency department and inpatient costs in the CI-CDS group, we will use similar methods to assess whether total costs of care, including all outpatient care and pharmacy, are also lower.

Analyses of secondary and exploratory patient outcomes will also follow the same analytic approach as the H1 model with appropriate modifications to the link function and error distribution.

